7.3 TREATMENT COMPLIANCE

Only listings are planned for this section of the report, based on the TS.

It is not intended to list the compliance separately.

7.4 PRIMARY OBJECTIVE ANALYSIS

7.4.1 Main analysis

The study was prematurely terminated after run-in period. No PK parameter values were assessed. Therefore, no primary or secondary endpoint analyses will be performed.

[REDACTED]

[REDACTED]
[REDACTED]

7.5 SECONDARY OBJECTIVE ANALYSIS

7.5.1 Key secondary objective analysis

This section is not applicable as no key secondary objective has been specified in the protocol.

7.5.2 Secondary objective analysis

This section is not applicable as no secondary objective has been specified in the protocol.

7.6 FURTHER OBJECTIVE ANALYSIS

Pharmacokinetic endpoints

The study was prematurely terminated after run-in period. No PK parameter values were assessed. Therefore, no descriptive analyses of PK endpoints will be performed.

Safety endpoints

For a description of the analysis of safety and tolerability, please refer to [Section 7.8](#).

7.7 EXTENT OF EXPOSURE

The date and time of drug administration will be listed for each subject.

7.8 SAFETY ANALYSIS

All safety analyses will be performed on the TS.

The safety data for treated subjects who failed to complete the study (dropouts or withdrawals) will be reported as far as their data are available. All withdrawals will be documented and the reason for withdrawal recorded.

7.8.1 Adverse Events

AEs will be coded using MedDRA. The coding version number will be displayed as a footnote in the respective output.

Unless otherwise specified, the analyses of AEs will be descriptive in nature. All analyses of AEs will be based on the number of subjects with AEs and NOT on the number of AEs. BI standards as presented in “Analysis and Presentation of Adverse Event Data from Clinical Trials – Display Template” (7) and “Analysis and Presentation of AE data from clinical trials” (8) will be applied.

The analysis of AEs will be based on the concept of treatment emergent AEs. That means that all AEs will be assigned to ‘screening’, ‘on-treatment’ or ‘follow-up’ phases as defined in [Section 6.1](#). AEs will be analysed based on actual treatments, as defined in [Table 6.1: 1](#).

According to the clinical study protocol, adverse events of special interest (AESI) will be analysed:

Section 5.2.6.1.4 of the CTP:

The following are considered as AESIs:

- Potential severe DILI

A potential severe Drug Induced Liver Injury (DILI) that requires follow-up is defined by the following alterations of hepatic laboratory parameters:

- *An elevation of AST (aspartate aminotransferase) and/or ALT (alanine aminotransferase) ≥ 3 -fold ULN combined with an elevation of total bilirubin ≥ 2 -fold ULN measured in the same blood sample, or in samples drawn within 30 days of each other, or*
- *Aminotransferase (ALT, and/or AST) elevations ≥ 10 -fold ULN*

These lab findings constitute a hepatic injury alert and the subjects showing these lab abnormalities need to be followed up according to the ‘DILI checklist’ provided in the ISF. In case of clinical symptoms of hepatic injury (icterus, unexplained encephalopathy, unexplained coagulopathy, right upper quadrant abdominal pain, etc.) without lab results (ALT, AST, total bilirubin) available, the Investigator should make sure that these parameters are analysed, if necessary in an unscheduled blood test. Should the results meet the criteria of hepatic injury alert, the procedures described in the DILI checklist should be followed.

According to ICH E3 (9), in addition to Deaths and serious adverse events, ‘other significant’ AEs need to be listed in the clinical trial report. These will be any non-serious adverse events

that led to an action taken with study drug (e.g. discontinuation or dose reduced or interrupted).

An overall summary of adverse events will be presented.

The frequency of subjects with AEs will be summarised by primary system organ class (SOC) and preferred term (PT). Separate tables will be provided for subjects with serious AEs, for subjects with drug-related AEs, for subjects with drug-related serious adverse events and for subjects with AESIs. In addition, the frequency of subjects with AEs will be summarised by worst intensity, primary system organ class (SOC) and preferred term (PT).

The system organ classes will be sorted by default alphabetically, PTs will be sorted by descending frequency (within SOC).

In addition, frequencies of subjects with non-serious AEs that had an incidence of $> 5\%$ for at least one treatment will be summarised by primary SOC and PT.

7.8.2 Laboratory data

Only listings will be provided for laboratory data and will be based on BI standards as presented in “Handling, Display and Analysis of Laboratory Data” (10). Analyses will be based on normalised values, which means transforming to a standard unit and a standard reference range. The original values will be analysed if the transformation into standard unit is not possible for a parameter.

Laboratory data will be analysed qualitatively via comparison of laboratory data to their reference ranges. Values outside the reference range as well as values defined as possibly clinically significant will be flagged in the data listings.

Clinically relevant findings in laboratory data will be reported as baseline conditions (at screening) or as AEs (during the trial) if judged clinically relevant by the investigator, and will be analysed as such.

It is the investigator's responsibility to decide whether a lab value is clinically significantly abnormal or not (prior to DBL).

7.8.3 Vital signs

Only listings will be presented for vital signs (blood pressure and pulse rate). The change from baseline will also be displayed.

Clinically relevant findings will be reported as baseline conditions (at screening) or as AEs (during the trial) if judged clinically relevant by the investigator, and will be analysed as such.

7.8.4 ECG

Clinically relevant abnormal findings will be reported as adverse events.
No separate listing or analysis of continuous ECG monitoring will be prepared.

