#### 5.2.4 Electrocardiogram

Twelve-lead ECGs (I, II, III, aVR, aVL, aVF, V1 - V6) will be recorded using a computerised electrocardiograph (CardioSoft EKG System, at the times provided in the Flow Chart.

c41232811-04 Trial Protocol Page 46 of 84

Proprietary confidential information © 2023 Boehringer Ingelheim International GmbH or one or more of its affiliated companies

To achieve a stable heart rate at rest and to assure high quality recordings, the site personnel will be instructed to assure a relaxed and quiet environment, so that all subjects are at complete rest.

All ECGs will be recorded for a 10 sec duration after subjects have rested for at least 5 min in a supine position. ECG assessment will always precede all other trial procedures scheduled for the same time to avoid compromising ECG quality.

All ECGs will be stored electronically on the Muse CV Cardiology System (
. Electrode placement will be performed according to the method of Wilson, Goldberger and Einthoven.

All locally printed ECGs will be evaluated by the investigator or a designee. Abnormal findings will be reported as AEs (during the trial) or baseline conditions (if identified at the screening visit) if assessed to be clinically relevant by the investigator. Any ECG abnormalities will be carefully monitored and, if necessary, the subject will be removed from the trial and will receive the appropriate medical treatment.

ECGs may be repeated for quality reasons (for instance, due to alternating current artefacts, muscle movements, or electrode dislocation) and the repeated ECG will be used for analysis. Additional (unscheduled) ECGs may be collected by the investigator for safety reasons.

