Adverse events will be coded using the Medical Dictionary for Regulatory Activities (MedDRA). Frequency, severity, and causal relationship of AEs will be tabulated by treatment, system organ class, and preferred term. SAEs, AESIs (see Section 5.2.6.1), and other significant AEs (according to ICH E3) will be listed separately.

Previous and concomitant therapies will be presented without consideration of time intervals and treatment periods.

Laboratory data will be compared to their reference ranges. Values outside the reference range will be highlighted in the listings. Additionally, differences from baseline will be evaluated.

Vital signs or other safety-relevant data will be assessed with regard to possible on-treatment changes from baseline.

In general, unless otherwise specified in the TSAP, the last non-missing measurement prior to first trial medication intake will be used as baseline for safety variables (laboratory data, ECG, vital signs).

Relevant ECG findings will be reported as AEs.

Results regarding the C-SSRS will only be listed.

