4. CHANGES IN THE PLANNED ANALYSIS OF THE STUDY

This trial has been prematurely terminated during the run-in period as Boehringer Ingelheim decided not to continue with trial execution due to strategic reasons. None of the subjects has started with treatment period 1. Therefore, not all analyses as planned in the CTP will be performed. For all study endpoints listings will be provided. Tables will only be provided for adverse events (AEs). For variables regarding disposition, demography, medical history, concomitant medication and non-drug procedures, exposition, protocol deviations, laboratory data, vital signs and C-SSRS suicidality, only listings will be provided and no descriptive analysis will be carried out. An additional analysis set, the Entered set, will be defined as a base for the disposition listings.

The descriptive and model-based analysis of pharmacokinetic endpoints will not be performed as well, in line with the CTP no PK samples were collected in the run-in period.

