7. PLANNED ANALYSIS

Safety analysis (refer to [Section 7.8](#)) will be performed by [REDACTED] and will be presented in Sections 15.3 and 15.4 of the CTR and in Appendix 16.2 and 16.1.13.1.

The study was prematurely terminated after run-in period. Therefore, in 15.3 and 15.4 only AEs will be presented. In addition, no descriptive data analysis of PK endpoints and concentrations will be performed.

The format of the listings and tables will follow the BI standards (see “Standards for Reporting of Clinical Trials and Project Summaries” [\(6\)](#)).

The individual values of all subjects will be listed, sorted by subject number and visit. The listings will be included in Appendix 16.2 of the CTR.

Units of variables should be given in the titles or column/row descriptors in brackets (e.g. (mg)).

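### Does SAP 7.8.4 leave the 12-lead ECG, a declared safety endpoint, without a listing?

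*SAP*

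**What the plan says.** SAP Section 5.3 carries over five safety and tolerability endpoints from Protocol Section 2.2.2.3: adverse events, safety laboratory, 12-lead ECG, vital signs and C-SSRS.

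SAP Section 4, written after the early termination, gives the general rule "For all study endpoints listings will be provided" and limits tables to adverse events. It then names variables for which descriptive analysis is withdrawn, ending with "laboratory data, vital signs and C-SSRS suicidality, only listings will be provided". ECG is not named there. SAP Section 7 adds that "The individual values of all subjects will be listed, sorted by subject number and visit", with the listings placed in Appendix 16.2.

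SAP Section 7.8.4 has two sentences: "Clinically relevant abnormal findings will be reported as adverse events", and "No separate listing or analysis of continuous ECG monitoring will be prepared".

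In the protocol, Section 5.2.4 describes the recordings: "All ECGs will be recorded for a 10 sec duration after subjects have rested for at least 5 min in a supine position". Section 7.2.5 gives the reporting rule "Relevant ECG findings will be reported as AEs". It also says that the last non-missing value before first intake "will be used as baseline for safety variables (laboratory data, ECG, vital signs", so ECG counts as a safety variable with a baseline.

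**The concern.** Sections 7.8.2 (laboratory), 7.8.3 (vital signs) and 7.9 (C-SSRS) of the SAP each state a listing. Section 7.8.4 does not. Its only statement about listings concerns a kind of ECG that the protocol never performs, which suggests text not fitted to this trial. Together with the absence of ECG from the Section 4 enumeration, this could lead a programmer to produce no ECG output at all.

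A declared safety endpoint would then be visible only through findings the investigator judged clinically relevant. Smaller shifts between Screening and end of study, including in QTc, would not be shown, although QT prolongation is an explicit eligibility criterion. An undeclared departure from the protocol in the one domain still being reported would be a fair criticism.

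**Working it through.** No estimate, interval or error rate depends on this point, so the check is a comparison of the text plus a count.

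**1. What each safety endpoint gets**

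| Endpoint (SAP 5.3) | Specific statement | General rules (SAP 4 and 7) |
|---|---|---|
| Adverse events | Tables and listings (SAP 4, 6.1, 7.8.1) | apply |
| Laboratory | Listing (SAP 7.8.2) | apply |
| Vital signs | Listing with change from baseline (SAP 7.8.3) | apply |
| C-SSRS | Listing (SAP 7.9) | apply |
| 12-lead ECG | Relevant findings become adverse events (SAP 7.8.4) | apply; no exception stated |

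ECG is the only row without a listing of its own. It is not a row with a listing refused, because the refusal in 7.8.4 is confined to continuous monitoring.

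**2. What the two possible readings produce**

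- *The general rules govern.* ECG is an endpoint under 5.3, so its individual values are listed in Appendix 16.2.
- *ECG is reported through adverse events and baseline conditions only.* This follows the reporting rule for ECG findings in Protocol 5.2.4 and 7.2.5. Values judged not relevant are not shown.

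Under both readings, relevant on-trial findings enter the adverse event tables, which are the only tables planned. The tables are identical.

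**3. How many recordings are involved**

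- Treated subjects: 28, all in the run-in only (SAP 6.1).
- The Flow Chart schedules ECGs at Screening, Day 22 of Periods 1 and 2, and end of study. No subject started Period 1 (SAP 4), which leaves Screening and end of study.
- Upper bound: 28 x 2 = 56. Of these, 28 are screening recordings made before any dose, so at most 56 - 28 = 28 could show a change on trial.
- End-of-study attendance is not confirmed. Protocol 6.2.3 says only that subjects who stop early should have that visit.

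**4. Screening findings**

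SAP 7.8.4 does not repeat that relevant abnormalities found at Screening are baseline conditions, as Protocol 5.2.4 and SAP 7.8.2 and 7.8.3 do. The investigator makes that classification under the protocol. Even if such a finding were entered as an adverse event, SAP 6.1 would assign it to the screening phase, which is left out of the Section 15.3 tables.

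**The case for a change.** The strongest opposing argument is that either reading exposes a defect. If the general rules cover ECG, Section 7.8.4 and the Section 4 enumeration fail to carry them out. If ECG was meant to be an exception, Section 4 is where it should have been declared. Protocol 7.2.5 gives ECG a baseline and foresees assessing other safety-relevant data for change on treatment, which could include ECG. Exposure to the contraceptive was real, and the protocol's risk table names ECG among the monitoring measures for thromboembolic risk. One listing would cost little.

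Much of this stands as a remark on drafting: the wording is inconsistent, and the inconsistency is not a product of redaction. It does not show that data go unreported. Section 4 names the variables for which no descriptive analysis will be carried out. The protocol gave ECG no separate descriptive analysis beyond the general provision on safety-relevant data, so its absence from that list may be deliberate. SAP 7.9 treats physical examination in the same way, through history and adverse events without a separate listing, which makes that intention plausible. Nor do the documents show that ECG intervals were captured as data at each visit, so the loss of QTc shifts is a supposition.

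**Conclusion.** No change to the plan is called for. The word *continuous* in SAP 7.8.4 is a clerical slip, and the missing ECG listing statement is a detail that the general rules in SAP Sections 4 and 7 already supply. An analyst who follows them lists the scheduled ECGs. One who follows the protocol's ECG reporting rule presents relevant findings as adverse events or baseline conditions. Neither course gives a wrong result, and the adverse event tables are the same.

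The size is at most 56 recordings, at most 28 of them after dosing, assuming full attendance at both visits. The safety endpoint is framed around BI 1358894, which no subject received (SAP 6.1), and SAP 7.4.1 confirms that no primary or secondary analysis remains. The conclusion rests on relevant findings being recorded as the protocol requires. It would need another look only if ECG had been a focus of the remaining analysis, or if the SAP had expressly refused a 12-lead listing; neither is the case.

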7.9 OTHER ANALYSIS

Physical examination

Physical examination findings will be reported as relevant medical history/baseline condition (i.e., a condition already existent before intake of trial drug) or as AE and will be summarised as such.

No separate listing or analysis of physical examination findings will be prepared.

Columbia Suicide Severity Rating Scale (C-SSRS)

Suicidality assessment with the C-SSRS will be assessed as additional safety parameter, measured at screening and at the end of study, due to the premature termination of trial. The results will be listed only. If applicable, the following sentence will be sufficient: No subjects with suicidal ideation, suicidal behaviour, or self-injurious behaviour without suicidal intent.

[REDACTED]

[REDACTED]

[REDACTED]

[figure not shown]
[REDACTED]

8. TIMEPOINT OF RELEASE OF TREATMENT INFORMATION

Not applicable due to open label fashion of the trial as described in the CTP section 4.1.5.

11. HISTORY TABLE

Table 11: 1 History table

Version	Date (DD-MMM- YY)	Author	Sections changed	Brief description of change
1.0	19-Mar-24	[REDACTED]	None	This is the final TSAP.
